AD can be categorized as sporadic AD (SAD) or familial AD (FAD) based on family history. FAD requires a patient with AD to have at least one first-degree relative diagnosed with AD or mild cognitive impairment (MCI) due to AD, and was reported to account for 12.50% to 25.00% of all AD cases [4,5]. FAD greatly contributes to AD research. First, it encompasses the physiological and pathological characteristics of all cognitive stages from preclinical to MCI to dementia. Second, it represents an ideal population, with a possible predictable age at onset (AAO), which is relatively young and has minimal complications (such as cerebrovascular disease), and facilitates exploration of the pathogenesis of AD. Third, it promotes the development of transgenic animal models with which anti-dementia drugs are tested.

FAD includes autosomal dominant AD (ADAD) [6], caused by mutations of genes including the amyloid precursor protein gene (*APP*), presenilin 1 gene (*PSEN1*), and presenilin 2 gene (*PSEN2*), which have been targeted by the Dominantly Inherited Alzheimer Network (<https://dian.wustl.edu/>); the E280A Antioquia cohort study[7]; and FAD cohorts, including those in France[8], England[9], Japan[10], South Korea[11], Finland[12], and so on. To date, 289 *PSEN1*, 48 *PSEN2*, and 58 *APP* mutations have been identified (<https://www.alzforum.org/mutations>), most of which were first reported in Caucasians. In Chinese, our team reported the first variant (NM_000021.3: c. 289G>T V97L in *PSEN1*) [13]. Several studies have since investigated the genetics of FAD: one study identified four variants in *PSEN1* and one variant in *APP*, and the detection rate of variants in *PSENs/APP* was 18.75% [14]. Another identified two variants in *APP*, eight variants in *PSEN1*, and three variants in *PSEN2*, and the detection rate of variants in *PSENs/APP* was 8.80% [15]. However, these cohorts were not multicentric and the sample sizes were relatively small; thus, the findings did not fully represent the mutation spectrum of FAD in China.

As one of the early interventions of AD and dementia, non-pharmacologic treatment (NPT) has been studied more and more in recent years [16]. At present, the NPT research on dementia mainly focuses on improving the lifestyle, physical exercise [17], music [18], cognitive training, risk factor control and

so on. Physical exercise as a common NPT method can improve the cognitive function of MCI patients and slow down the progression of AD [19, 20]. Physical exercise may improve cognitive function through oxidative stress, inflammation, metabolism and other mechanisms [21], and affect the brain structure related to dementia, such as hippocampus/parahippocampal area, anterior cingulate gyrus and prefrontal cortex. Music therapy can improve some cognitive functions of mild AD patients, especially episodic memory, executive function and general cognition, and also has a positive impact on mental and psychological health [22]. Cognitive training can delay the onset of symptoms and improve the A β related memory deficit by preventing oxidative stress and changing the plasticity of white matter in the brain [23, 24]. In addition, functional task training [25], lifestyle intervention [26], Mediterranean diet (MeDi) [27], psychosocial intervention [28], and improving sleep quality [29] are also effective ways to improve cognitive function. At present, most of the NPT studies have a single sample, lack of quantitative and objective evaluation criteria, do not exclude other influencing factors (other comorbid diseases, gender, etc.). Furthermore, their neurobiological mechanism is not clear. It is necessary to explore the efficacy and potential neurobiological mechanism of NPT in AD and dementia through well-designed randomized controlled trials, and systematic and effective intervention programs.

Therefore, [name]'s team relied on Xuanwu Hospital of Capital Medical University and many research institutes and hospitals aim to establish the Chinese Familial Alzheimer's disease network (CFAN). CFAN is a nationwide, multi-center, large-scale longitudinal observational research cohort. It will help to collect genetic information, clinical characteristics, cognition, neuroimaging, and biological specimen data of FAD to promote research progress on new mutations identification, pathogenesis mechanism and biomarkers.

Recently, in our study, 3330 patients with AD or mild cognitive impairment in 514 pedigrees were enrolled from the CFAN. 13.12% of pedigrees carried *PSENs/APP* missense mutations, 3.71% carried *PSENs/APP* synonymous/untranslated region variants, and 83.17% did not carry *PSENs/APP* mutations. In the present study, 11 missense mutations were first identified by the CFAN, including 10 in *PSEN1* and one in *APP*. The present study highlights that the FAD population in China needs extensive investigation, and a concerted effort is necessary to identify the crucial pathological genes underlying the pathogenesis of AD.

2. Introduction

2.1 Overview

CFAN is the world's second largest registry network started by [name] in 2005. The sponsor of this project is Xuanwu Hospital of Capital Medical University. CFAN is a multicenter observational longitudinal cohort study. The main research population for CFAN are autosomal

dominant inherited AD and unknown gene mutation AD family. All CFAN participants will be assessed longitudinally with comprehensive clinical, cognitive, genetic, imaging, and biomarker examinations, and all data will be collected using a unified standard, and stored into a central database. The purpose of the establishment of CFAN is to advance the research progress of FAD new mutations, pathogenic mechanisms and biomarkers in the Chinese population. At the same time, CFAN has great clinical significance. Through gene screening of the family, asymptomatic gene carriers can be found earlier, early diagnosis and intervention can be performed, and the prognosis can be improved. Long-term follow-up of asymptomatic gene carriers is convenient to further reveal the evolution of AD disease, and to find a breakthrough for early diagnosis and intervention in the population of asymptomatic gene carriers.

2.2 Research sites

There is a total of 68 research centers participating in this project, involving 26 provinces and cities. For details, please refer to Appendix 16.

2.3 Research period

The research period of this project is from February 2005 to January 2038 or longer.

2.4 Sample size

There will be a total of 40,000 subjects participating in this project. The total number of subjects to be included in this hospital is 5,000, and other sites include 400-600 persons per sites.

3. Research aims

This research will establish and continuously improve the FAD research network in conjunction with multi-center institutions nationwide. By collecting information on the family's demography, genetics, neuropsychology, neuroimaging, biomarkers and other information, we can understand the current FAD population in China, clarify the genetic characteristics, pathogenesis, disease characteristics and diagnosis and treatment status of AD in China; which will lay the foundation for ameliorating clinical diagnosis and treatment, establishing a Chinese FAD clinical database and an international cooperative research platform.

3.1 To set up a multi-center, nationwide FAD research network and database platform in China

The network and database include ADAD cohort of the known mutations of *PSEN1*, *PSEN2* and *APP* (mutation carriers and noncarriers; pre-symptomatic and symptomatic) and unknown mutations cohort.

3.2 To clarify the epidemiological characteristics of FAD in China.

Conduct a comprehensive FAD epidemiological survey in China to clarify the impact of different nationalities, regions, gender, age, living environment (rural/urban), education level, etc. on the

occurrence and development of the disease.

3.3 To clarify the genetic characteristics of FAD in China.

This project is to discover new FAD mutation sites, pathogenic genes, to protective genes, to explore the pathogenic and protective mechanism, to analyze the disease development laws of families with different sizes of FAD in China, and to clarify the frequency distribution of mutant genes in the Chinese FAD population.

3.4 To clarify the clinical characteristics and disease development laws of FAD in China.

The project will collect and regularly follow-up the samples (blood, urine and saliva etc.) and data (neuropsychology, imaging etc.) in the cohort. Emphasis is placed on the occurrence and development of asymptomatic mutant gene carriers from asymptomatic to symptomatic periods.

3.5 To discover and verify the early diagnosis biomarkers of AD.

In the FAD family cohort, we will screen high-sensitivity and high-specificity body fluid markers suitable for Chinese people, verify in the SAD cohort, and establish a prediction model of body fluid markers for AD occurrence and disease progression; use structural MRI, dual tracer ^{18}F -FDG PET and ^{11}C -PIB PET multimodal imaging technology, dynamically monitor the dynamic evolution of imaging biomarkers such as brain structure, glucose metabolism and $\text{A}\beta$ deposition at various stages of AD progression.

3.6 To establish a genetic counseling model.

We will combine with the genetic characteristics of Chinese FAD to analyze the impact of lifestyle, physical exercise, nootropic drugs, cognitive training, etc. on the disease progression of FAD patients or asymptomatic mutant gene carriers, to establish a genetic counseling model.

4. Research content

4.1 Cohorts

We recruit Pre-MCI, MCI and AD dementia patients and normal cognitive control people to establish horizontal and vertical research cohorts, including ADAD cohort and the unknown mutation carrier cohort. Establish a national FAD research network and electronic database platform to improve the clinical information database and biological sample database.

4.2 Epidemiological characteristics of FAD in China

Investigate the basic information of the cohort, including individual factors such as sociodemography, lifestyle, past medical history, vascular risk factors, occupational exposure, and external environmental factors such as socioeconomic level. Conduct a comprehensive FAD epidemiological survey in China to identify the impact of nationality, region, gender, age, living environment (rural/urban), education level, etc. on the occurrence and development of the disease.

4.3 Genetic characteristics and mechanism of FAD in China

Based on the early recruitment and registration of FAD, the disease development laws of Chinese FAD families of different sizes will be analyzed. Each family must meet the characteristics of co-segregation. Use the latest sequencing technology to find new genes and new mutation sites in the disease-causing genes (*APP*, *PSEN1*, *PSEN2*) that have been discovered. Explore differences in gene frequency from those reported in the West. Determine the frequency distribution of *APOE* genotypes and *APOE* alleles (*APOEε4*, *APOEε3*, and *APOEε2*), and explore the frequency and incidence of *APOE* genes in FAD population in China. All the above research will provide new evidence for risk assessment and intervention in the early stages of the disease.

4.4 Clinical characteristics, disease development process and laws of FAD in China

Clinical examination including medical history, past history, family history, physical examination and neurological examination will be performed. Neuropsychological assessment usually includes cognitive function assessment (memory assessment, attention/executive function assessment, language function assessment, visual space and structural ability, calculation), non-cognitive assessment (mental behavior change) and evaluation of daily functions (personal life ability, social ability, work ability), etc. It is evaluated by the following unified and standardized neuropsychological scales: Mini-Mental State Examination, MMSE; Rey-Osterrieth Complex Figure Test, ROCFT; Digit Span Backward, DSB; Digit Span Forward, DSF; Verbal Fluency Test, VFT; Trail Making Test A/B, TMT A/B; Boston Naming Test, BNT; Clinical Dementia Rating, CDR; Neuropsychiatric Inventory Questionnaire, NPI-Q; Hamilton Anxiety Scale, HAMA; Hamilton Depression Scale, HAMD; Activities of Daily Living, ADL. In addition, Modified Hachinski Ischemic Scale (m-HIS) was used to distinguish AD from VaD.

Through baseline and follow-up observation, we will analyze cognitive function, mental behavior symptoms and daily living ability of asymptomatic mutant gene carriers in FAD families. We will focus on the period from the asymptomatic to the development of symptoms, including subtle neuropsychological, clinical symptoms, changes in imaging, blood, cerebrospinal fluid, urine and saliva.

4.5 Biomarkers of FAD in China

We will conduct neuropsychological tests, clinical examinations, and imaging examinations on members of the FAD family, and conduct regular cerebrospinal fluid and blood sample collections. Use the international standardized electronic patient registration system to establish a large-scale and high-quality clinical information database and biological sample database to provide a foundation and platform for the establishment of the AD diagnosis system and risk prediction model. We will also focus on the asymptomatic mutant gene carriers in FAD families and analyze the changes of various imaging and body fluid markers in normal cognitive, Pre-MCI, MCI, AD and other stages.

4.5.1 Body fluid markers

Firstly, by collecting biological specimens of FAD family members, including blood, cerebrospinal fluid, urine and saliva etc., and referring biological sample banks of people in different clinical stages, the study can effectively identify highly sensitive and highly specific body fluid markers in different clinical stages of AD. Furthermore, longitudinal follow-up of people in different clinical stages of the family, detect AD potential and newly developed biomarkers in body fluids at baseline, and then combined with clinical neuropsychological evaluation, to establish a diagnosis system for AD clinical stages. Moreover, conduct regular follow-up and collection of body fluid samples in the included research cohort to monitor the dynamic changes of body fluid markers of patients as the disease progresses. Finally, combined with individual factors, clinical characteristics, neuropsychological assessment and body fluid markers, a comprehensive risk analysis of the entire disease process of AD occurrence and development was carried out, and body fluid marker prediction models in different stages of AD pathogenesis were established.

4.5.2 Image markers

We follow up the subjects with normal cognitive, Pre-MCI, MCI, AD stages in the FAD family, and test the hippocampus atrophy and cortical thickness of the subjects by MRI. We also detect eight observation brain regions by ^{18}F -FDG PET (bilateral frontal lobe, bilateral temporal lobe, bilateral parietal lobe, bilateral hippocampus). We will obtain accurate registration image data of patients' brain structure, metabolic function, pathological protein molecule deposition at various stages of AD progression. We will determine the quantitative critical thresholds for the early diagnosis of AD by ^{18}F -FDG PET and ^{11}C -PIB PET. Then we will obtain highly sensitive imaging markers for the early diagnosis of AD.

4.6 Research on early intervention and diagnosis and treatment of AD

Regularly follow up the non-onset members of the FAD family members, combined with the genetic characteristics of Chinese FAD, analyze the effects of lifestyle, physical exercise, nootropic drugs, cognitive training, etc. on the disease progression of FAD patients or asymptomatic mutant gene carriers. Investigate the effects of early non-pharmacological intervention on delaying the progression of the disease. Pay close attention to the cognitive situation of carriers of asymptomatic gene mutations. Once symptoms are found, intervene immediately to prevent disease progression. Early diagnosis of AD in the asymptomatic stage will provide a good time window for clinical intervention and treatment, and is expected to reverse and contain the development of dementia.

5. Research Technology Route

[figure not shown]

Figure1. Research technology route of CFAN study

6. Research Process

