6.5 Baseline visit

The baseline study visit includes the following items:

(1) Explain study contents and procedures to participant and sign the informed consent form.

(2) Urine pregnancy test (for women of childbearing potential).

(3) Check inclusion/exclusion criteria.

(4) Blood, urine and saliva samples collection (biomarkers).

(5) Genetic testing to examine risk gene *APOE* and known pathogenic genes *PSEN1*, *PSEN2*, and *APP* for all participants.

(6) Collecting participant and informant demographics.

(7) Collecting family history and draw family tree.

(8) Previous medical, medication history and life style.

(9) Physical exam and vital signs.

(10) Neurological Exam.

(11) Neuropsychological test: Mini-Mental State Examination (MMSE), Montreal Cognitive Assessment (MoCA), Neuropsychiatric Inventory Questionnaire (NPI-Q), Hamilton Anxiety Scale (HAMA), Hamilton Depression Scale (HAMD), Modified Hachinski Ischemic Scale (m-HIS), the world health organization university of California-Los Angeles auditory verbal learning Test (WHO-UCLA AVLT), Rey-Osterrieth Complex Figure Test (ROCFT), Digit Span Forward (DSF), Digit Span Backward (DSB), Verbal Fluency Test (VFT), Trail Making Test (TMT) A/B, Boston Naming Test (BNT), Clinical Dementia Rating (CDR), Activities of Daily Living (ADL).

(12) MRI includes the following: conventional scan T1 weighted image (T1WI), T2 weighted image (T2WI), T2 FLAIR and hippocampal scan coronary T1-FLAIR sequence.

(13) ¹⁸F-FDG PET.

(14) ¹¹C-PIB PET.

(15) Carotid ultrasound.

(16) Lumbar puncture to examine cerebrospinal fluid (after MRI exams) and follow-up phone call (if participate in LP)

(17) After informed consent, non-pharmaceutical interventions are carried out on non-onset gene mutation carriers in the family, including lifestyle changes, increased physical exercise and cognitive training, and nootropic drugs.

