7.4.3 Carotid ultrasound

Carotid ultrasound can clearly demonstrate the vascular intima-media thickness, the location and size of plaque, the degree of vascular stenosis, and analyze hemodynamics. It plays a key role in the assessment and diagnosis of vascular-related diseases caused by atherosclerosis. Carotid ultrasound examination should be performed within 1 month before or after neuropsychological examination (with no new vascular disease event). An experienced ultrasound physician is required to perform the operation according to "Guidelines for Carotid Ultrasound Examination". Longitudinal and transverse

section scanning are performed from frontal and lateral directions. Observe and record the peak systolic velocity (PSV), end diastolic velocity (EDV), intima-media thickness (IMT) and plaque (diameter, number, acoustic properties) of internal carotid artery, common carotid artery and carotid bifurcation.

8. Statistical analysis

Periodic review of the accumulating data will be made to safeguard the statistical quality of the data and to ascertain whether they conform to the expectations of the original statistical design. At the same time, the statistician will perform statistical quality control of FAD data, focusing on outlier and missing data detection and comparison among sites. Then, the statistician will participate in statistical data analyses, consultations and reporting using R software and other statistical software, such as SAS and SPSS for specialized statistical analyses. The sample size is calculated using the paired sample t test, and the statistical test level is set to 0.05.

The normality and homogeneity of variance tests were performed on continuous variables. Data that passed these two tests were presented as mean \pm standard deviation, then underwent t-testing for comparisons between two groups and one-way analysis of variance (ANOVA) testing for comparisons among three or more groups. After ANOVA analysis, a Dunnett's multiple comparison test was used for post hoc testing. Data that did not pass the normality test were presented as quartiles, and underwent nonparametric testing, using the Kruskal-Wallis test and Dunn's multiple comparison test for comparisons among three or more groups. The significance of differences was assessed by the χ^2 test for categorical variables. The correlation between variables were calculated using Pearson or Spearman method.

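### Sections 3.6 and 4.6 aim to estimate intervention effects on progression, but the observational cohort ties intervention to symptoms, carrier status or consent and defines no comparable untreated carriers

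*Protocol*

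**What the plan says.** Two places state an aim about effect. Section 3.6 will "analyze the impact of lifestyle, physical exercise, nootropic drugs, cognitive training, etc. on the disease progression of FAD patients or asymptomatic mutant gene carriers", and the result is to support a genetic counselling model. Section 4.6 goes further: "Investigate the effects of early non-pharmacological intervention on delaying the progression of the disease".

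Two places say when intervention begins.
- Section 4.6, on carriers being watched for symptoms: "Once symptoms are found, intervene immediately to prevent disease progression".
- Section 6.5 item 17, at the baseline visit and after consent: "non-pharmaceutical interventions are carried out on non-onset gene mutation carriers in the family". The item lists lifestyle change, exercise, cognitive training and nootropic drugs.

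Section 2.1 describes the study in these words: "CFAN is a multicenter observational longitudinal cohort study". The protocol mentions no randomisation, delayed start or concurrent untreated carrier group. On planning, section 8 says only: "The sample size is calculated using the paired sample t test, and the statistical test level is set to 0.05". The longitudinal model in section 8 contrasts mutation carriers with noncarriers along estimated years to onset.

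**The concern.** Delaying progression is a statement about cause. To support it, treated people must be compared with people who would otherwise have progressed in the same way. Here one route to intervention is the first sign of the outcome itself, and the other is carrying the mutation that drives the outcome. If item 17 is followed, the asymptomatic carriers left untreated are those who declined. Noncarriers are not expected to progress.

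Any effect estimate then mixes what the intervention does with why it was given. Section 3.6 would carry that estimate into the counselling of mutation carriers, so a wrong sign would matter in practice.

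**Working it through.** The protocol gives no planning figure for the intervention aim, so there is none to reproduce. The check asks what each available contrast would show if the intervention did nothing.

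**First illustration: contrasts between groups.** All inputs are assumptions, not figures from the protocol.
- Higher score is worse, and follow-up is 3 years.
- Carrier onset is uniform over years 0 to 6.
- Yearly worsening is *a* before onset (0 or 0.1) and *b* after onset (0.2 to 1.5).
- Residual SD is 0.8, and noncarriers do not change.

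Carriers with onset within 3 years spend on average 1.5 years after onset. Half of all carriers have onset in that window, so the average over all carriers is 0.75 years. Expected 3-year change is then:
- carriers with onset in follow-up: 1.5a + 1.5b
- carriers not yet symptomatic: 3a
- all carriers: 2.25a + 0.75b
- patients symptomatic throughout: 3b

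| Contrast, true effect zero | Formula | Smallest | Largest | Significant at two-sided 0.05 |
|---|---|---|---|---|
| Started at onset vs not yet symptomatic | 1.5(b − a) | 1.5 × 0.1 = +0.15 | 1.5 × 1.5 = +2.25 | 38% to 100% |
| Carriers treated at baseline vs noncarriers | 2.25a + 0.75b | 0.75 × 0.2 = +0.15 | 0.225 + 1.125 = +1.35 | 63% to 100% |
| Carriers treated at baseline vs symptomatic patients | 2.25(a − b) | 2.25 × (−0.1) = −0.23 | 2.25 × (−1.5) = −3.38 | 93% to 100% |
| Carriers split at random | 0 | 0 | 0 | 4% to 7% |

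Positive values look like harm and negative values like benefit. The last column comes from simulation with 300 carriers and 1,000 replicates per scenario. Its mean differences agree with the formulas to within 0.01.

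**Second illustration: before versus after within a person.** Again all inputs are assumptions.
- Lower score is worse, as on the MMSE.
- Mean slope is −0.5 to −1.5 points per year, with SD between people of 0.7 to 1.0.
- Measurement SD is 1.
- Intervention starts at the first annual visit in years 1 to 3 that shows a drop of 2 or more points. The last score is at year 5.

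With no treatment effect:
- 50% to 87% become treated.
- Their true slope is about 0.9 to 1.6 points per year worse than that of people never triggered. This looks like harm.
- In the treated, mean observed change is −1.8 to −2.4 points per year before the trigger and −0.7 to −1.6 after it. This looks like benefit.

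The second pattern is regression to the mean: the trigger picks visits at which the measured score happened to be low. The same data thus give opposite signs under two contrasts.

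**The case against.** Several points on the other side have force.

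- **Direction.** A reader might infer that the design makes an ineffective intervention look harmful. The documents do not support one direction. The protocol never names the contrast it will run, and the only test named for planning is a within-person one, for which the illustration shows false benefit.
- **No untreated comparison at all.** That is too broad. The aims also cover FAD patients, and item 17 covers only mutation carriers without symptoms. Section 1 reports that 83.17% of pedigrees carried no PSENs/APP mutation. In those families lifestyle and drug use vary naturally and are recorded (section 6.5 item 8; section 7.1.4). Such comparisons are confounded, but they exist. What is missing is a comparable untreated group among carriers.
- **Components inseparable.** Item 17 lists components. It does not say that every carrier receives all of them, so it cannot be concluded that none has a contrast of its own.
- **The protocol's own standard.** Section 1 says of non-pharmacologic treatment: "It is necessary to explore the efficacy and potential neurobiological mechanism of NPT in AD and dementia through well-designed randomized controlled trials". This is background on the field and not a rule for this cohort. It does show that the authors see where efficacy evidence should come from.
- **The SAP.** Adjustment for confounders and time-varying exposure may be set out in an SAP not shown, and their absence here is no finding. An SAP cannot, however, supply a comparison group that the design does not create.

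The sizes are also open to challenge. Section 6.6 brings visits forward on reported cognitive change, not on a score threshold.

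**Conclusion.** The point holds in a limited form. An effect on progression is a stated aim, and both routes to intervention follow prognosis, carrier status or consent. No concurrent, comparable untreated carriers are defined. An intervention with no effect could therefore appear harmful or beneficial, and the sign depends on the contrast chosen.

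This conclusion rests on the protocol's text. The sizes rest on assumed slopes, SDs, onset times and trigger, and are not estimates for this study. The genetic, epidemiological and biomarker aims do not depend on an intervention contrast and are outside this point. The aims should be corrected because their result is meant for counselling.

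**What to change.** 1. Restate sections 3.6 and 4.6, and the counselling model, as the association of recorded exposures with later progression. Make no claim that intervention delays progression, and leave efficacy to a separate randomised study.
2. For participants free of symptoms at enrolment, use exposure recorded before any reported cognitive change. Do not use intervention begun at or after symptom detection to estimate an effect.
3. That rule cannot apply to patients already symptomatic at enrolment. For them, report associations descriptively, adjusted for baseline severity.
4. State that carrier-versus-noncarrier and before-after differences will not be read as intervention effects. Baseline intervention under item 17 meets the rule in step 2 but stays tied to carrier status and consent, so it too supports association only.
5. The sponsor must reconcile sections 2.1, 4.6 and 6.5 item 17 on whether, and when, intervention is part of the study. No clinical rule is proposed here.

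The cost is the wording of two aims, one analysis rule and a weaker claim than the current text makes.
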